- i. Clinical labs, hematology, serum chemistry (including creatinine, blood urea nitrogen, creatinine clearance calculation [if available], estimated glomerular filtration rate [eGFR] calculation [if available]), and concomitant AED levels (fosphenytoin/phenytoin, valproic acid, levetiracetam, lacosamide, phenobarbital, or brivaracetam, if collected per standard of care) and Routine Urinalysis (including urine protein, and microscopic examination, if any abnormal value is observed on the urine dipstick test) should be collected predose (screening), if unable to collect predose, collect within 2 hours following IP initiation. Collect at the time of IP discontinuation (+/- 1 hour), either at the end of the taper or if the IP administration is stopped without a taper and 24 hours (+/- 1 hour) following IP discontinuation and at the time of hospital discharge. Collect at the weekly follow-up visits (Week 1, 2, 3, or 4) for hospitalized participants and for participants who have been discharged (whenever possible). For participants who terminate early from the study, collect at the time of early termination (whenever possible). Collect in the event of an SAE. The investigator may collect at any other time based on clinical judgment.
- j. Urine chemistry sample for N-acetyl- β -D-glucosaminidase (NAG), β 2-microglobulin, and creatinine should be collected predose (screening), if unable to collect predose, collect within 2 hours following IP initiation, 24 hours (+/- 1 hour) following IP discontinuation and at the time of hospital discharge. Collect at one of the weekly follow-up visits (Week 1, 2, 3, or 4) for hospitalized participants and when possible, for participants who have been discharged. For participants who terminate early from the study, collect at the time of early termination (whenever possible). Urine samples will be stored frozen unless otherwise dictated or revised in the Biospecimen Manual.
- k. Clinical coagulation (including fibrinogen, activated partial thromboplastin time [APTT], prothrombin time [PT] and international normalize ratio [INR]) should be collected predose (screening), if unable to collect predose, collect within 2 hours following IP initiation, 24 hours (+/- 1 hour) following IP discontinuation and at the time of hospital discharge. For participants who terminate early from the study, collect at the time of early termination (whenever possible). The investigator may collect at any other time based on clinical judgment.

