6.2.4 Investigational Product Infusion Precautions

Throughout the study, heart rate and rhythm, blood pressure, and oxygen saturation are monitored. Investigational product may be temporarily or permanently discontinued, if clinically indicated, for treatment of persistent hypotension (sustained systolic blood pressure <90 mmHg), cardiac arrhythmia or oxygen desaturation.

Due to Captisol® presence in the IV formulation of the IP, renal function will be monitored throughout the study. In addition to standard and accepted biomarkers of renal function (i.e., creatinine clearance and estimated glomerular filtration ratio [eGFR]), urinary exploratory biomarkers of renal function (N-acetyl-β-D-glucosaminidase [NAG], β2-microglobulin, and creatinine) will be monitored throughout the study and reviewed by the DMC.

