7.2.3.7 Clinical Laboratory Evaluations

All clinical laboratory assays will be performed according to the institution's laboratory normal procedures. If there are laboratory collections that are not done by the institution's laboratory, the institution should follow their standard procedures for sending samples to their reference laboratories for analysis (e.g., AEDs). The collection timepoints are detailed in [Table 1](#). Reference ranges are to be supplied by the laboratory and will be used to assess the clinical laboratory data for clinical significance and out of range pathologic changes. The investigator should assess out of range clinical laboratory values, indicating if the values are clinically significant or not clinically significant. Abnormal clinical laboratory values that are unexpected or not explained by the participant's clinical condition may, at the discretion of the investigator or Sponsor, be repeated as soon as possible until confirmed, explained, or resolved.

Urine Chemistry

Urine samples for N-acetyl- β -D-glucosaminidase (NAG), β 2-microglobulin, and creatinine will be collected at the times specified in Table 1. Urine samples will be stored frozen. Details regarding sample collection, processing, storage, and shipment to the bioanalytical vendor are described in the Biospecimen Manual.

Drugs of Abuse Testing

A urine or serum sample for drugs of abuse testing should be collected per the institution standard of care and prior to IP initiation. A urine or serum sample for alcohol testing should be collected if medically indicated. If medically indicated, the investigator may expand testing for additional drugs of abuse above the institution's standard of care. If unable to collect predose, collect as soon as possible following IP initiation. However, if a participant tests positive, it will be at the investigator's discretion to weigh the risks versus benefits for enrollment or continued participation. If the investigator decides to discontinue the IP, refer to [Section 4.5](#).

Pregnancy Test

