1.2.5 Safety Endpoints

- Vital signs (height, weight, blood pressure [BP], pulse, respiratory rate [RR], body temperature, oxygen saturation).
- Electrocardiogram (ECGs).
- Clinical laboratory tests (hematology, chemistry and urinalysis, pregnancy and drug test).
- Physical exam findings.
- Use of concomitant medications.

Adverse events.

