3.3.3 Laboratory Evaluations

All laboratory parameters will be presented in Standard International (SI) units. Only scheduled lab parameters will be included in the lab summaries.

Laboratory data collected in this study include serum chemistry and hematology values, urinalysis results, pregnancy results, and drug of abuse results. The baseline laboratory value is defined as the last value observed prior to IP initiation. Any values collected after IP initiation are regarded as post-baseline. Change from baseline will be calculated as the post-baseline value minus the baseline value. Only the numeric part in laboratory values that contain non-numeric qualifiers, such as less than (<) a certain value or greater than (>) a certain value, will be used in the summary statistics.

Quantitative results (including actual value and change from baseline) will be summarized using descriptive statistics by baseline and post-baseline visit for each laboratory test based on the Safety Population. Shift tables cross-tabulating the baseline and post-baseline classifications (below [L], Normal [N], or above [H] the reference range), by visit, will be provided.

All laboratory data will be included in the listing, including whether the value was below (L), within (N), or above (H) the normal reference range (some urinalysis labs are assigned only normal and abnormal classifications).

Pregnancy results performed on selected participants will be listed.

Screening results for drugs of abuse, including alcohol, will be listed separately.

All blood gas results, including FiO₂, PaO₂, and arterial pH, if available will be listed.

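### SAP 3.3.3 would summarise urine NAG and beta-2-microglobulin only as raw concentrations and should use the urine creatinine from the same sample to correct them for dilution

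*SAP*

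**What the plan says.** Protocol 6.2.4 gives the reason for renal monitoring: "Due to Captisol® presence in the IV formulation of the IP, renal function will be monitored throughout the study". Alongside creatinine clearance and eGFR it names "urinary exploratory biomarkers of renal function": NAG, beta-2-microglobulin "and creatinine) will be monitored throughout the study and reviewed by the DMC". Protocol 7.2.3.7 repeats the three analytes, ending "and creatinine will be collected at the times specified in Table 1". Table 6 in that section gives Urine Chemistry its own heading, separate from Urinalysis and Biochemistry, and gives Coagulation its own heading too. Protocol 10.5 commits to summarising clinical laboratory tests by treatment group.

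SAP 1.2.5 lists the laboratory safety endpoints as "Clinical laboratory tests (hematology, chemistry and urinalysis, pregnancy and drug test". SAP 3.3.3 lists the data as "Laboratory data collected in this study include serum chemistry and hematology values, urinalysis results, pregnancy results, and drug of abuse results". Neither names urine chemistry or coagulation. SAP 3.3.3 then gives a general rule: every quantitative laboratory test is described by visit, as observed value and as change from baseline. It adds that all laboratory data go into a listing. The SAP schedule (Appendix 8.1, urine chemistry row and footnote j) carries NAG and beta-2-microglobulin but not urine creatinine. SAP section 4 declares no departures from the protocol.

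**The concern.** A urinary marker concentration depends on how much marker the kidney releases and on how much water it is released into. Neither document describes a timed or volume-corrected urine collection, so a change in raw NAG or beta-2-microglobulin between two samples mixes the two. Urine creatinine from the same sample is the obvious means of separating them. The protocol collects it, but neither document defines a variable that uses it.

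What is at stake is how readable one exploratory panel will be. If the tables show only raw values and raw changes, a shift in dilution can look like a renal change, or can blur a real one, in the markers chosen because of the excipient.

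**Working it through.** No sample size, power or alpha figure is involved. The check compares the texts and adds one line of algebra.

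**1. Which panels the SAP names.** Protocol Table 6 against SAP 1.2.5 and 3.3.3:

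| Protocol Table 6 panel | Named in the SAP laboratory text? |
|---|---|
| Hematology | yes |
| Biochemistry | yes (as serum chemistry in 3.3.3) |
| Urinalysis | yes |
| Pregnancy, drugs of abuse | yes |
| Coagulation | no |
| Urine chemistry (NAG, beta-2-microglobulin, creatinine) | no |

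Antiepileptic drug levels, measured only where local practice calls for them, are not named either; they do not bear on this point.

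**2. Whether the unnamed panels are still covered.** They are, on the better reading. The opening sentence of 3.3.3 is not a closed list: blood gases are absent from it but are handled later in the section. The general summary rule applies to every laboratory test, the listing takes in all laboratory data, and SAP 2.1 puts all summary tables by treatment group. Protocol 10.5 makes the same commitment, and SAP section 4 declares no change from it.

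**3. What that coverage produces.** Observed value and change from baseline. Marker-to-creatinine variables defined in either document: none.

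**4. Effect of dilution.** Let A be the excretion rate of the marker, K that of creatinine and V the urine flow.

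- Raw marker concentration = A/V
- Urine creatinine concentration = K/V
- Ratio = (A/V)/(K/V) = A/K

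If flow changes by a factor d while A and K stay the same, the raw concentration changes by 1/d - 1 and the ratio by 0. The documents give no value for d, so a range is assumed:

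| Assumed d | Raw concentration | Marker/creatinine ratio |
|---|---|---|
| 0.5 (more concentrated) | 1/0.5 - 1 = +100% | 0% |
| 1 | 0% | 0% |
| 2 (more dilute) | 1/2 - 1 = -50% | 0% |

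The same two-fold shift gives +100% one way and -50% the other. On the log scale it is symmetric, which is why a ratio to baseline should be summarised there.

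**5. Whether urine creatinine exists.** It appears in the protocol synopsis, Table 1 with footnote j, 6.2.4, 7.2.3.7 and Table 6. It is missing from the SAP schedule row and footnote j. The protocol's amendment log places its addition in the October 2023 amendment, whereas the planned study period began in August 2020. Participants enrolled before the change may have no urine creatinine. The documents do not give the number who do; the 100 randomised is only an upper bound.

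**6. Baseline.** Protocol Table 1 footnote j allows the first urine chemistry sample up to 2 hours after infusion start when a predose sample is not possible. SAP 3.3.3 takes baseline as the last value before infusion start and counts anything later as post-baseline. A participant whose first sample falls in that 2-hour window therefore has no baseline, and so no change or ratio to baseline. Footnote k gives coagulation the same allowance.

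**The case against.** The other side has a good case. The protocol itself calls the urinary markers exploratory. Serum creatinine and BUN, with eGFR and creatinine clearance where available, sit in Biochemistry and get summaries and shift tables under SAP 3.3.3. Adverse events are tabulated by system organ class and preferred term, and the urinary markers go to the DMC during the trial. The missing urine creatinine in SAP footnote j looks like an outdated copy of the schedule. The SAP appendix refers readers to the protocol for schedule details, so collection is not affected. No passage says that urine creatinine was collected for normalisation; that is an inference. Table templates, programming specifications and the Biospecimen Manual are separate files and might already provide corrected values.

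Most of this stands, and it rules out three stronger readings that a reader might infer:

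- **That the renal markers go unanalysed or drop out of the safety comparison.** The general rule, the listing and Protocol 10.5 reach them. The missing panel names are a gap in wording.
- **That raw values would be too noisy to show a difference.** Neither document gives a variance, and the two-fold dilution change is an assumption. In a randomised comparison, dilution noise costs precision; it does not by itself remove a difference.
- **That about 100 urine panels could be corrected.** That is the number randomised. Given the date on which urine creatinine was added, the number with paired values is probably smaller and cannot be derived from the documents.

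What the objection does not answer is the method. If the general rule governs, the SAP specifies raw value and raw change. A DMC review or a listing does not replace a by-arm summary that separates excretion from dilution.

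**Conclusion.** The point holds as a low-priority improvement to the safety analysis. As written, SAP 3.3.3 would report NAG and beta-2-microglobulin only as raw values and raw changes, although the current protocol collects urine creatinine with them. The size is conditional: for an assumed 0.5- to 2-fold change in dilution, raw values move by +100% to -50% and the ratio does not move. This assumes that marker and creatinine excretion are unchanged between samples, and that no timed or volume-corrected collection is specified in manuals not available here.

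Naming urine chemistry and coagulation, and correcting the SAP schedule, is housekeeping. The co-primary and key secondary tests are not touched.

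**What to change.** In SAP 3.3.3:

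- Define NAG/creatinine and beta-2-microglobulin/creatinine from the same urine sample. Summarise them descriptively by arm as ratio to baseline on the log scale, at 24 hours after IP discontinuation and at hospital discharge.
- Report the number of participants with paired urine creatinine, and show raw values for the rest.
- State how a first sample taken up to 2 hours after infusion start is treated: either as baseline for this panel, with the number of such participants shown, or as post-baseline with baseline missing.

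As housekeeping, name urine chemistry and coagulation in SAP 1.2.5 and 3.3.3, and add urine creatinine to the urine chemistry row and footnote j of SAP Appendix 8.1 so that they match the protocol.

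The cost is some SAP wording and a few extra tables, with no new sampling. The drawback is that ratios will be available for fewer than all participants, so corrected and raw summaries will rest on different subsets and must be labelled as such.

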As described in [Table 1](#) and [Section 4.4](#), a urine or serum pregnancy test should be collected for all females of childbearing potential prior to IP initiation, and if pregnancy is suspected. If unable to collect predose, collect as soon as possible following IP initiation. Enrollment is not contingent upon results. However, if a participant has a positive test result, it will be at the investigator's discretion to weigh the risks versus benefits for continued participation. If the investigator decides to discontinue the IP, please refer to [Section 4.5](#). If the institution requires the pregnancy test results be obtained prior to IP initiation, the institution guidelines will be followed.

Blood Gas

All blood gas samples arterial or venous, if collected, will be at the investigator's discretion to manage care. If collected from the time of SE diagnosis through the end of the first 24 hours of the follow-up period, the eCRF should be completed. If samples are not collected, a sample will not be required.

If a decision is made to intubate the participant between IP initiation through the end of the first 24 hours of the follow-up period, a blood sample should be collected. The sample should be collected immediately prior to or as close as possible to the time of intubation.

The clinical laboratory tests performed as part of the protocol are listed in Table 6.

Table 6. Clinical Laboratory Tests

Hematology	Coagulation	Biochemistry	Urinalysis
Hemoglobin (Hb)	Fibrinogen	Sodium	pH
Hematocrit (Hct)	Activated partial thromboplastin time (aPTT)	Potassium	Protein
Red blood cell count (RBC)	Prothrombin time (PT)	Calcium	Blood
White blood cell count; total and differential (WBC)	International normalized ratio (INR)	Glucose	Ketones
Mean corpuscular hemoglobin (MCH)		Total protein	Glucose
Mean corpuscular hemoglobin concentration (MCHC)		Albumin	Bilirubin
Mean corpuscular volume (MCV)		Creatinine	Specific gravity
Platelet count		Blood urea nitrogen (BUN)	If any abnormal value is observed on the urine dipstick test, the sample should be further analyzed with urine microscopy:
WBC Differential		Total Bilirubin	WBC
% Basophils		Alkaline phosphatase (ALP)	RBC
% Eosinophils		Aspartate transaminase (AST)	Cellular casts
% Lymphocytes		Alanine transaminase (ALT)	Granular casts
% Monocytes		Total cholesterol ¹	Hyaline casts
% Neutrophils		Estimated Glomerular Filtration Rate (eGFR), if available	

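### If a local laboratory reports eGFR with an upper limit, the SAP's rule for qualified values understates decline in the eGFR summary

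*SAP*

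**What the plan says.** SAP 3.3.3 (Laboratory Evaluations) deals with results carrying a < or > sign in one sentence: "Only the numeric part in laboratory values that contain non-numeric qualifiers" "will be used in the summary statistics". The same section says "Change from baseline will be calculated as the post-baseline value minus the baseline value". It makes no exception for eGFR.

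Protocol 7.2.3.7 leaves the testing to the sites: "All clinical laboratory assays will be performed according to the institution's laboratory normal procedures". Table 6 in that section lists "Estimated Glomerular Filtration Rate (eGFR), if available", and creatinine clearance carries the same condition. Serum creatinine and blood urea nitrogen do not. Neither document names an eGFR equation or a reporting format. About 100 sites are planned (Protocol 3.4, SAP 2.4).

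Protocol 6.2.4 ties the renal monitoring to the excipient: because Captisol is in the IV formulation, "renal function will be monitored throughout the study". It names creatinine clearance and eGFR as the standard markers, and adds urinary NAG, β2-microglobulin and creatinine, which the data monitoring committee reviews.

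**The concern.** The two standard renal markers named in Protocol 6.2.4 are the least standardised laboratory data in the trial: local, conditional on availability, and with no common equation. If a laboratory prints high eGFR results only as above a limit, the SAP rule turns that limit into a measurement. A participant with good kidney function at entry is then recorded at the cap, and a later fall is measured from the cap instead of from the true starting point. Where a decline occurs, the error runs in one direction, towards no change.

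Sites that do not report eGFR add nothing to the eGFR summary at all. At stake is the reliability of one descriptive safety table on a question that the protocol itself raises.

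**Working it through.** The plan states no figure on this point, so there is nothing to reproduce. The check applies the SAP rule directly.

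**Inputs from the documents.** The numeric-part rule and the change formula (SAP 3.3.3); local assays and conditional eGFR (Protocol 7.2.3.7); entry eGFR nominally 45 or above, because exclusion criterion 9 removes stage 3B and worse (Protocol 4.2).

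**Assumption.** The cap. The documents give none, so 60 and 90 are both shown.

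**Formula.** Analysed value r(x) = min(x, cap). Change shown = r(post) - r(baseline). True change = post - baseline.

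**Step 1: single participants.**

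| True eGFR | True change | Shown, cap >60 | Shown, cap >90 |
|---|---|---|---|
| 110 to 62 | -48 | 60 - 60 = 0 | 62 - 90 = -28 |
| 110 to 58 | -52 | 58 - 60 = -2 | 58 - 90 = -32 |
| 120 to 91 | -29 | 60 - 60 = 0 | 90 - 90 = 0 |
| 120 to 44 | -76 | 44 - 60 = -16 | 44 - 90 = -46 |

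A fall that stays above the cap disappears. A fall through the cap is reduced but still visible. A value of 44 or less is printed as a number under either cap.

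**Step 2: group means.** This is a hypothetical simulation, not a forecast. Baseline eGFR is normal with SD 25, truncated at 45; one arm falls by 20% or 40%; both arms have 10% log-scale noise; every participant's laboratory is capped. Entries are the difference between arms in mean change, with the share of the true difference kept.

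| Baseline mean (before truncation) | Fall | True | Cap >60 | Cap >90 |
|---|---|---|---|---|
| 75 | 20% | -16.2 | -3.5 (22%) | -11.7 (72%) |
| 75 | 40% | -32.3 | -11.8 (37%) | -26.9 (83%) |
| 90 | 20% | -18.5 | -1.9 (10%) | -9.9 (54%) |
| 90 | 40% | -37.0 | -8.0 (22%) | -25.9 (70%) |
| 105 | 20% | -21.2 | -0.8 (4%) | -7.2 (34%) |
| 105 | 40% | -42.4 | -4.5 (11%) | -22.6 (53%) |

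**Step 3: share of sites affected.** If a share s of otherwise similar participants comes from capped laboratories, difference shown = (1 - s) × true + s × capped. For baseline mean 90, a 20% fall and a >60 cap:
- s = 0: -18.5, no distortion.
- s = 0.5: 0.5 × (-18.5) + 0.5 × (-1.9) = -10.2.
- s = 1: -1.9.

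**Step 4: what serum creatinine would show.** If eGFR varies as creatinine to the power -k, fold rise = (baseline eGFR / post eGFR)^(1/k). For 120 to 61, which a >60 cap shows as 0, (120/61)^(1/k) is 1.97 for k = 1 and 1.76 for k = 1.2. The information lost from the eGFR table is therefore still present in creatinine.

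**The case against.** The strongest objection is that the trigger is not in the documents. Nothing says that any site caps eGFR, and where exact values are reported the rule does nothing. That stands, and it makes the point conditional.

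The second objection is that other renal outputs remain. Serum creatinine and blood urea nitrogen are collected without the availability condition and summarised as value and change. Shift tables by visit and full listings are planned. Investigators judge out-of-range results. The data monitoring committee reviews the urinary markers. This also stands, with limits. The shift tables use only low, normal and high, so a large fall within the normal range moves no category. No table of fold change in creatinine is planned, so a few participants with a marked rise can be diluted in a mean. Listings do not compare the arms. SAP 3.3.3 does not name the urinary markers among its laboratory data.

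Third, a result printed only as >60 is lost at the laboratory, and no substitution rule can restore it. That is correct, and it is why the remedy has to go back to creatinine.

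A reader might go further and infer that the rule hides renal harm, that every participant with normal baseline function is misread, or that the eGFR exclusion and withdrawal example are compromised. The documents support none of these. The creatinine data remain. A participant who is stable above the cap correctly shows 0. Neither the exclusion (Protocol 4.2) nor the example at 44 or less (Protocol 4.5.2) uses SAP summary statistics.

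**Conclusion.** The point holds in conditional form. Where local eGFR is capped, SAP 3.3.3 sets the value to the cap and the eGFR summary understates decline. Under the hypothetical inputs above, with all sites capped, the table keeps 4% to 37% of the true difference between arms for a >60 cap and 34% to 83% for a >90 cap. With no capped sites it keeps all of it. The cap, the affected share, the baseline distribution and the size of the fall are all assumptions. Separately, and without any assumption about caps, eGFR may be missing from some sites because it is collected only if available.

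This is a gap in safety reporting for one descriptive parameter. It is worth closing because the protocol names eGFR as a standard marker for its own excipient concern and the repair is cheap.

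**What to change.** In SAP 3.3.3:

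- Derive eGFR at every scheduled timepoint from the collected serum creatinine, age and sex, with one prespecified adult equation and one paediatric equation (using height where collected). Base the eGFR tables on this derived value.
- Keep local eGFR in listings only, and report the number of capped values.
- Add a by-arm table of maximum serum creatinine ratio to baseline, for example 1.5 times or more and 2 times or more.
- Do not simply drop > values from local eGFR means. That would selectively remove the normal results.

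The cost is one derivation program, one extra table and a few lines of SAP text, with no new data from sites: date of birth and sex are recorded (Protocol 7.2.1) and creatinine is in the chemistry panel. Two limits remain. Height is collected predose only if feasible (Protocol 7.2.3.4), so it may be late or missing for some participants under 18. And a participant whose first creatinine is drawn after IP initiation, which Protocol Table 1 allows within 2 hours, has no baseline under the SAP definition, so no change or ratio can be calculated for that participant.
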